#### Table 1. Full List of Analytic Datasets for Two Study Exposures and One Calibration Exposure

Notes: IP = Inpatient Setting; ED = Emergency Department Setting; AV = Ambulatory Care Setting. Risk Window is set to Days 1-28 for all analytic datasets.

An example analytic dataset is shown with simulated data in **Table 2**. The Analytic Dataset ID is directly mapped to the list above. The original diagnosis captures the incident ICD-9-CM or ICD-10-CM code captured prior to mapping and the leaf level node represents the mapped value. The time of the outcome is relative to the incident study drug exposure that is always indexed as Day 0. The number of counts is the number of times this particular code was observed with this particular relative timing in the study.

Table 2. Sample Analytic Bataset with Simulated Bata						
Analytic	Original	Original	Leaf Level	Leaf Level	Relative Time	Counts
Dataset ID	Diagnosis	Diagnosis Type	Node	Node Type	of Outcome	
1	250	9	250	9	-15	3

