#### 2. Information Component Temporal Pattern Discovery:

Information Component Temporal Pattern Discovery (ICTPD) is another longitudinal signal detection method that can be applied to self-controlled designs. ICTPD uses a shrinkage estimator to reduce the number of false positives due to random variability (and then indirectly the multiple comparisons) or due to very low expected values for rare adverse events or exposures. It does not explicitly control for multiplicity. The information component with shrinkage  $IC_{\Delta}$  can be calculated as shown below. The more general formula allows for accounting of censoring between the risk window and control window, but this study will require overall enrollment in both. There is a closed form solution for the credibility interval of the  $IC_{\Delta}$ .

$$IC_{\Delta} = \log_2 \left( \frac{y_1 + \frac{1}{2}}{y_0 \left( \frac{E_1}{E_0} \right) + \frac{1}{2}} \right)$$

Where:  $y_1$  = number of outcomes in the risk window among study exposure of interest

 $y_0$  = number of outcomes in the comparison window among study exposure of interest

 $E_1$  = number of outcomes in the risk window among the external calibration exposure of interest

 $E_{0}$  = number of outcomes in the comparison window among the external calibration exposure of interest  $% \left( {{E_{0}}} \right) = {E_{0}} \right)$ 

ICTPD makes use of an external calibration mechanism to control for global patterns of healthcare utilization that may account for systematic differences between pre- and post- exposure windows. It has a similar intention to the conditional Bernoulli version of the tree scan statistic described above but is implemented differently. The conditional Bernoulli version of the tree-based scan statistic utilizes the pattern of outcome occurrence in the entire MLCCS tree to control for global patterns of healthcare. The ICTPD uses an external exposure group – specifically, all exposures using all dispensing or prescription

records – and then performs the adjustment in a node-specific fashion. Using node-specific notation similar to the equations above, the  $IC_{\Delta}$  can be re-written below:

$$IC_{\Delta} = \log_2\left(\frac{c_G + \frac{1}{2}}{n_G\left(\frac{C_G}{N_G}\right) + \frac{1}{2}}\right)$$

where: G = node of interest

 $c_{\rm G}$  = number of cases in the risk window for a given node G among the study exposure of interest

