 $n_{G}$  = number of cases in the comparison window for a given node G among the study exposure of interest

 $C_{G}$  = total number of cases in the risk window for a given node G among the calibration exposure population

 $N_G$  = total number of cases in the comparison window for a given node G among the calibration exposure population

In our study, access to all dispensing records (i.e., a "general" population) is not feasible so we will randomly select 100 NDC and HCPCS codes and combine their data to create our "calibration exposure."

The traditional alerting threshold for the ICTPD method uses a 2-sided 95% credible interval, denoted  $IC_{\Delta 025}$ . An alert occurs only when this value is positive, implying that an alert is only raised for an unusual elevation in the frequency of observed outcomes in the risk window. The indication function in the test statistic for TreeScan performs the same function. For this analysis, we will observe the number of alerts when  $IC_{\Delta 025} > 0$  and when  $IC_{\Delta 01} > 0$ .

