#### 3. Sequence Symmetry Analysis:

Sequence Symmetry Analysis (SSA) is a tool used for rapid detection of potential adverse drug events associated with newly marketed medicines utilizing computerized claims data. SSA is based on analyzing the sequences of medications and events; if an event occurs more frequently after exposure to a medication than before, it may be an indication of an adverse effect of the medication. The method uses a simple sequence-based algorithm (pre-post) and is relatively straightforward computationally. In patients with both exposure and outcome during the defined observation window, the crude sequence ratio = # with exposure before outcome/# with outcome before exposure. SSA does not control for multiple hypothesis tests across many outcomes. A prior study ranked SSA alerts based on magnitude of absolute difference in sequence orders and presented unadjusted p-values from chi-square tests. SSA will not be performed with any of the scenarios that include a post-exposure comparison window.

Traditionally, SSA does not utilize a threshold for alerts, and instead examines a pre-specified metric – e.g., the ranked magnitude of absolute difference – across all outcomes. With thousands of outcomes, such an examination is impractical. Therefore, we propose to take the maximum total number of alerts arising from analogous TreeScan or ICTPD analyses and use that value as cut-off point for SSA outcomes of interest. For example, if a particular analytic dataset gives rise to 5 alerts with ICTPD and 7 alerts with TreeScan, then we will look at the top 7 magnitudes of absolute difference.

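### ICTPD treats the calibration ratio from one random draw of 100 codes as a known constant, so its alerts depend on that draw, and the printed formula fails where calibration counts are zero

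*Protocol*

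**What the plan says.** Protocol section III.F.2 describes the ICTPD reference group as "specifically, all exposures using all dispensing or prescription" records, and says that the method "performs the adjustment in a node-specific fashion". Because access to all dispensing records is not feasible, "we will randomly select 100 NDC and HCPCS codes and combine their data to create our" calibration exposure.

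C_G is defined as the "total number of cases in the risk window for a given node G among the calibration exposure" population, and N_G as the "total number of cases in the comparison window for a given node G among the calibration exposure" population. Both are pooled totals. The expected count is n_G(C_G/N_G), and ½ is added to the observed and the expected count. No term carries uncertainty in C_G/N_G, and nothing is said about zero counts. An alert is raised when IC025 > 0; IC01 > 0 is also tallied.

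The caption of Table 1 reads "Full List of Analytic Datasets for Two Study Exposures and One Calibration Exposure". The calibration exposure has 15 datasets (3 comparison windows × 5 combinations of washout, tree level and care setting), and these serve both study drugs. Section III.F.3 sets the SSA cut-off in the pre-exposure scenarios: it will "take the maximum total number of alerts arising from analogous TreeScan or ICTPD analyses".

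**The concern.** The ratio C_G/N_G is an estimate from a sample, but the formula uses it as a constant. Two sources of error are left out: which 100 codes were drawn, and the Poisson-type noise in C_G and N_G themselves. An error in the ratio shifts IC by an almost fixed amount that does not shrink as study-drug counts grow.

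The study exists to compare three methods. If ICTPD's alert list depends on one draw, part of any difference from TreeScan belongs to the draw and not to the method. Section III.G also records nodes that alert across several scenarios, but every ICTPD scenario for both drugs shares the same 100 codes, so agreement across scenarios does not test the draw. Through the cut-off rule, the draw can also change how many SSA outcomes are examined.

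At the sparse end the problem is no longer one of precision, because the printed formula returns a meaningless value or none.

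**Working it through.** The protocol gives no alert rate, code volumes or node counts for this step, so there is no stated figure to reproduce.

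**Inputs from the protocol:** the printed IC formula; 28-day risk and comparison windows, so the ratio is about 1 without utilization trends; alert if IC025 > 0 or IC01 > 0.

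**Assumed:**
- The lower limit is log2[gamma quantile(shape c_G + ½) / (E + ½)], with E = n_G·C_G/N_G. The protocol only cites the closed form.
- Study counts are Poisson.
- Code volumes are lognormal with log-SD σ.
- The code-to-code SD of ln(C_G/N_G) is τ.

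**1. How far a shift in the ratio moves an alert (c_G = 60, n_G = 40)**

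| C_G/N_G | IC | IC025 | IC01 |
|---|---|---|---|
| 1.00 | log2(60.5/40.5) = 0.579 | +0.191 | +0.116 |
| 1.10 | log2(60.5/44.5) = 0.443 | +0.055 | -0.020 |
| 1.25 | log2(60.5/50.5) = 0.261 | -0.128 | -0.203 |

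A 10% error removes the IC01 alert and a 25% error removes both.

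**2. How much the draw can move the ratio (100 codes, τ = 0.3)**

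| σ | Effective codes | Top-5 share | SD of ln ratio | 95% range about centre |
|---|---|---|---|---|
| 0 | 100 | 5% | 0.031 | 0.94–1.06 |
| 1 | 43 | 24% | 0.050 | 0.91–1.11 |
| 2 | 11 | 55% | 0.105 | 0.81–1.24 |
| 3 | 4.5 | 80% | 0.160 | 0.73–1.39 |

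If τ = 0, the draw has no effect at any σ.

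**3. Effect on null nodes**

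Discordance is the share of nodes alerting under either of two independent draws, on the same study data, that alert under only one.

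| Events per window | IC025 rate, SD 0 | SD 0.03 | SD 0.10 | Discordance, SD 0.03 | SD 0.10 |
|---|---|---|---|---|---|
| 20 | 8.3% | 8.3% | 9% | 16% | 42% |
| 50 | 8.3% | 8.5% | 10% | 24% | 58% |
| 300 | 8.3% | 9.6% | 19% | 50% | 77% |
| 1000 | 8.3% | 12% | 28% | 67% | 78% |

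The 8.3% floor comes from treating n_G as fixed. It is not due to the draw, and only the rise above it counts here. For a true rate ratio of 1.5 with 50 events in the comparison window and τ = 0.3, discordance is 7%, 9%, 18% and 25% at σ = 0, 1, 2 and 3.

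**4. Count noise in the calibration ratio alone (no draw effect, true ratio 1)**

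With a mean of 200, 50 or 10 calibration events per window, the 95% range of C_G/N_G is 0.82–1.22, 0.67–1.49 or 0.38–2.67. With a mean of 2, N_G = 0 has probability e^-2 = 13.5%; with a mean of 5, e^-5 = 0.7%.

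**5. Zero cells in the printed formula**

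- C_G = 0 makes E = 0 for any n_G. With c_G = 3 and n_G = 10, IC = log2(3.5/0.5) = +2.81 and, under the gamma interval, IC025 = +0.76 and IC01 = +0.31: an alert on both rules. At ratio 1, IC = log2(3.5/10.5) = -1.58.
- With C_G = 0, c_G = 2 gives IC025 = -0.27, so every node with 3 or more risk events alerts whatever n_G is.
- N_G = 0 divides by zero, so IC is undefined.

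**The case against.** The strongest reply has four parts.

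*Pooling by volume is correct.* The all-records reference is itself volume-weighted, so pooling randomly drawn codes estimates the same quantity with more variance. This stands: pooling is not the fault. Products used for a condition would also weigh heavily in that node under the full reference.

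*Dominance by a few codes is not shown.* A reader might infer that a handful of high-volume codes sets the ratio, and that codes are drawn with equal probability. The protocol says only that codes are selected at random and gives no volumes. Dominance is absent at σ = 0, mild at σ = 1 and clear only from about σ = 2. This stands too, but the draw still matters without skew: at SD 0.03, about the equal-weight case, discordance in null nodes is already 24% at 50 events.

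*The inflation is small in ordinary nodes.* A reader might take 19% or 28% as the general false-alert rate. Those figures need 300 or 1000 events per window; at 20 to 50 events the rate is 9–10%. The protocol gives no node counts, and 24 of the 30 study-drug datasets use inpatient and emergency settings only. This stands, and limits the claim to instability of the alert list, plus inflation in large nodes.

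*These details belong in an analysis plan or code list.* The sampling frame, seed and code list may well be there, and their absence is not counted. But the protocol itself fixes the single calibration group and prints a formula that, followed literally, gives false alerts at C_G = 0 and no value at N_G = 0.

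**Conclusion.** The point holds in a limited form. From the text alone: a single random sample of 100 codes supplies a node-specific ratio that is used as a constant for both drugs and every setting; its uncertainty is ignored; and the formula fails at zero calibration counts. The IC values at C_G = 0 and the undefined case at N_G = 0 need no assumption. The statement that 3 risk events suffice for an alert needs the gamma interval.

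The size of the draw effect rests on assumed volumes and code-to-code variation. At a log-ratio SD of 0.10, somewhat over half of null alerts at 50 events change with the draw, while the null alert rate rises by about two percentage points. With no variation between codes the draw has no effect. The documents do not support saying that a few codes do set the ratio, or that volume pooling aims at the wrong quantity.

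**What to change.** 1. State a rule for sparse calibration nodes: where C_G or N_G is zero or below a set minimum, use the ratio of the nearest ancestor node with adequate counts. List the nodes handled this way.
2. Keep the identifier of the drawn code in the calibration data (the sample layout in Table 2 has no such column). Resample the 100 codes by bootstrap or leave-one-code-out, report ICTPD alert counts with their range, and flag nodes whose alert status changes. Show the SSA cut-off over the same range where ICTPD sets it.

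The cost is one extra column in the extract, some additional analysis, and an ICTPD alert count that is less clear-cut. No new data source is needed. Resampling describes sensitivity to the codes drawn; it does not recover the all-records reference.

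Repeat draws, or selection in proportion to size, are optional and sensible only if code volumes are accessible. Size-proportional selection would not guarantee 100 effective codes within a node, and repeat draws would multiply the 15 calibration datasets.

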#### 3. Sequence Symmetry Analysis:

Sequence Symmetry Analysis (SSA) is a tool used for rapid detection of potential adverse drug events associated with newly marketed medicines utilizing computerized claims data. SSA is based on analyzing the sequences of medications and events; if an event occurs more frequently after exposure to a medication than before, it may be an indication of an adverse effect of the medication. The method uses a simple sequence-based algorithm (pre-post) and is relatively straightforward computationally. In patients with both exposure and outcome during the defined observation window, the crude sequence ratio = # with exposure before outcome/# with outcome before exposure. SSA does not control for multiple hypothesis tests across many outcomes. A prior study ranked SSA alerts based on magnitude of absolute difference in sequence orders and presented unadjusted p-values from chi-square tests. SSA will not be performed with any of the scenarios that include a post-exposure comparison window.

Traditionally, SSA does not utilize a threshold for alerts, and instead examines a pre-specified metric – e.g., the ranked magnitude of absolute difference – across all outcomes. With thousands of outcomes, such an examination is impractical. Therefore, we propose to take the maximum total number of alerts arising from analogous TreeScan or ICTPD analyses and use that value as cut-off point for SSA outcomes of interest. For example, if a particular analytic dataset gives rise to 5 alerts with ICTPD and 7 alerts with TreeScan, then we will look at the top 7 magnitudes of absolute difference.

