## III. METHODS

#### A. SURVEILLANCE POPULATION, ENROLLMENT CRITERIA AND STUDY EXPOSURES

Data will be obtained from Optum ClinInformatics from the years 2004 to 2016. We will include individuals who were dispensed the study exposures of interest on or after their 18th birthday during the available date range without further inclusion or exclusion criteria.

There are two study exposures of interest: oral forms of levetiracetam and lamotrigine used in the adult population. Additionally, there is one "calibration" exposure that must be collected to implement one of the methods. The two study exposures were chosen because they have relatively well-characterized safety profiles and are used primarily for treatment for seizure disorders which are medical conditions that are not usually associated with rapid changes in overall clinical status (except for rate of seizures itself). Stability in the expected underlying clinical status is especially important when implementing self-controlled designs to isolate the effect of the exposure itself rather than other temporal confounding factors (e.g., generally declining or improving health state), a concept described in epidemiology as exchangeability. Self-controlled designs compare time periods and it is only a fair comparison when factors outside of the incident dispensing of the study exposure are held as equal as possible through either design or analysis techniques. When the general risk of the health outcomes of interest is equivalent but for the study exposure, then the differences between the observed and expected rate beyond a predefined statistical threshold signifies a potential causal hypothesis requiring further investigation.

Although we will not assess outcomes in the period of time immediately preceding the incident dispensing of the study drug of interest, we still expect that both of these anti-seizure medications may show an increased frequency of seizure-related disorders in the pre-exposure comparison window. Nonetheless, we have chosen to include these outcomes within the groupings of outcomes being assessed. Lamotrigine also has other on- and off-label uses for mood disorders or pain that may create additional time-varying confounding by indication. We expect to triage any increased frequency of these adverse outcomes with these acknowledged limitations.

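### The SSA top-K rule ranks absolute differences without a direction restriction, so outcomes that fall after dispensing can take alert slots, and the unscaled difference favours common outcomes

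*Protocol*

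**What the plan says.** Section III.F.3 describes the SSA signal as directional: "if an event occurs more frequently after exposure to a medication than before, it may be an indication of an adverse effect". It defines a relative measure, "the crude sequence ratio = # with exposure before outcome/# with outcome before exposure", but does not use it for selection. It reports that "A prior study ranked SSA alerts based on magnitude of absolute difference in sequence orders" and says that SSA traditionally sets no threshold and "instead examines a pre-specified metric – e.g., the ranked magnitude of absolute difference – across all outcomes". The protocol then adds its own cut-off: "we propose to take the maximum total number of alerts arising from analogous TreeScan or ICTPD analyses". With 5 ICTPD alerts and 7 TreeScan alerts, "then we will look at the top 7 magnitudes of absolute difference".

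The other two methods are restricted to excesses. In section III.F.1 the TreeScan likelihood ratio carries an indicator that removes decreases. For ICTPD, section III.F.2 says that "an alert is only raised for an unusual elevation in the frequency of observed outcomes in the risk window" and notes that the TreeScan indicator does the same job.

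Section III.A expects that both drugs "may show an increased frequency of seizure-related disorders in the pre-exposure comparison window". SSA is run only with pre-exposure comparison windows (sections III.F and III.F.3). Section II.B makes outcome prevalence and strength of association the factors of the simulation.

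**The concern.** The direction rule is written down for two of the three methods and left out for the third. An absolute difference of 100 counts the same whether the outcome rose or fell, so anyone who programs the rule as worded will list falls as SSA findings. This matters most where SSA is applied, since the pre-exposure windows are where the protocol itself expects outcomes tied to the indication to be higher before dispensing. Because the list is capped at K, each fall that enters pushes out a rise.

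A second feature acts in the same direction. The difference is not scaled for how common the outcome is, so chance variation in a frequent code can outrank a strong excess in an uncommon one. If SSA then detects few uncommon outcomes in the simulation, a reader cannot tell whether the method or the ranking metric is responsible.

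**Working it through.** **The plan's own figure.** K = max(5, 7) = 7, as in the worked example.

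**Null variation of the metric.** The risk window is days 1-28 and the pre-exposure windows are 28 days (section III.E, Table 1), so under the null each event falls before or after with probability 0.5. With c events after, n before, D = c - n and T = c + n, the SD of D is sqrt(T): 4.5 at T = 20, 10 at T = 100, 44.7 at T = 2,000 and 100 at T = 10,000. This needs no assumption about the data beyond independent events.

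**Three illustrative outcomes** (LLR from Equation 1a with p = 0.5):

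| After / before | Ratio | Absolute D | D/sqrt(T) | LLR | One-sided p |
|---|---|---|---|---|---|
| 30 / 10 | 3.0 | 20 | 20/sqrt(40) = 3.16 | 5.23 | 0.001 |
| 2,060 / 2,000 | 1.03 | 60 | 60/sqrt(4,060) = 0.94 | 0.44 | 0.18 |
| 1,900 / 2,000 | 0.95 | 100 | -100/sqrt(3,900) = -1.60 | 0 | 0.95 |

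The literal SSA rule puts the third row first and the first row last. TreeScan orders them the other way round and gives the third row no weight.

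**Share of slots taken by decreases.** With no confounding, D is symmetric about zero, so decreases take half of the slots filled by null outcomes: 3.5/7 = 50% if the inserted outcome is not listed, and 3/7 = 43% if it is.

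**Simulation.** The protocol gives no event counts, so these are assumptions: 1,000 null outcomes with log-normal means (median 10 per window, log-SD 1.6, largest about 1,934), Poisson counts, one outcome with an inserted relative risk (RR), and 1,500 runs per setting. Decreases took 42-50% of the top 7, as the symmetry argument predicts. The chance that the inserted outcome is listed was:

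| Baseline events, RR | K | Absolute D (literal) | Signed D | Signed D/sqrt(T) |
|---|---|---|---|---|
| 5, RR 3 | 7 | 0.00 | 0.00 | 0.47 |
| 10, RR 3 | 7 | 0.01 | 0.12 | 0.83 |
| 20, RR 3 | 7 | 0.59 | 0.87 | 0.99 |
| 50, RR 2 | 7 | 0.82 | 0.95 | 0.96 |
| 100, RR 2 | 7 | 1.00 | 1.00 | 1.00 |
| 10, RR 3 | 20 | 0.23 | 0.61 | 0.91 |
| 20, RR 3 | 20 | 0.95 | 0.99 | 1.00 |

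The step from the third to the fourth column is the effect of direction; the step from the fourth to the fifth is the effect of scale.

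**With indication-related decreases.** Five outcomes with means of about 140-150 per window were halved after dispensing, as an assumed stand-in for the outcomes in section III.A. Decreases then took 73-83% of the top 7. For 20 baseline events and RR 3, the literal rule fell from 0.59 to 0.12, while signed D stayed at 0.87.

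**Sensitivity to the assumed counts.** For 10 baseline events, RR 3 and K = 7, the three rankings gave 0%, 0% and 78% with a null median of 19, and 21%, 54% and 86% with a null median of 3. Across the null counts and K tried, the literal rule ran from 0% to 88% for this outcome. For 100 events and RR 2 it was 95-100%.

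**The case against.** **Direction.** The protocol never says that decreases count as SSA alerts, and its description of the method implies interest in excesses. That is fair: the defect is an omitted restriction, not a declared two-sided rule. But the sentence that would be programmed is the ranking sentence, and it carries no sign.

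**Choice of metric.** Absolute difference is attributed to an earlier SSA screening study, and section III.G says that methods are taken as used in practice with small changes. If SSA as practised is weak for uncommon outcomes, a methods evaluation should report it. This stands as a reason to keep the metric. Moreover, with equal windows the LLR near the null is about D²/(2T), half the square of D/sqrt(T). Making a signed scaled difference the main ranking would turn SSA into a near copy of unconditional TreeScan without its multiplicity control.

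**Tempting stronger readings.** A reader might infer that SSA will miss inserted risks in rare outcomes, or that the ranking settles the power comparison in advance. The document does not support this, because it fixes no prevalence, relative risk or K. K = 7 is only an example, and ICTPD, which has no explicit multiplicity control, could push K higher. Some misses would also be shared: an exact test at 0.01/1,000, a rough proxy for TreeScan's adjusted threshold, detected only 0.01, 0.12 and 0.59 at RR 3 on 5, 10 and 20 events.

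**Seizure-related decreases.** These bear on the empirical analysis only. In the simulation the other outcomes are randomised to background rates, so there only chance decreases compete. In the empirical analysis, alerts will also be triaged as known or expected, which helps interpretation but does not bring back excesses pushed out of the top K.

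**Conclusion.** The concern holds for direction. As worded, the SSA rule admits decreases that the other two methods exclude by construction and that the protocol's own account of SSA does not seek. About half of the null slots go to decreases by symmetry alone. The higher share with confounding, and the displacement of true excesses, rest on assumed counts and on an assumed halving of five outcomes.

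The scale effect is real but conditional. That the null SD is sqrt(T) is arithmetic; how much detection it costs depends on event counts, relative risk and K. Under the assumed counts the loss can be large at about 10-20 baseline events with small K, and is small or absent at about 100 events with RR 2. This justifies a second ranking beside the planned one, not its replacement. The higher inclusion under the scaled ranking should not be read as a power gain over TreeScan, since a top-K list always names K outcomes whether or not any departs from chance.

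**What to change.** In section III.F.3, state that only outcomes with more events after than before exposure enter the SSA ranking and the top-K cut-off. This brings SSA into line with the TreeScan indicator and the ICTPD rule.

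Keep the absolute difference, so restricted, as the planned SSA ranking. Report beside it, as a sensitivity analysis, a frequency-scaled ranking with the same restriction and the same K, for example the lower confidence limit of the sequence ratio or the signed chi-square. Low SSA detection of uncommon outcomes can then be attributed to the ranking metric or to the method.

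The cost is one clause, a line of code and one extra ranking to report; no new data are needed. The small downside is that the sensitivity ranking will closely resemble unconditional TreeScan, which the report should say.
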